**Investigator Interests:**

Does the principal investigator, or do any research personnel who are responsible for the design, conduct or reporting of this project or any of their family members (spouse or dependent child) have an incentive or interest, financial or otherwise, that may affect the protection of the human subjects involved in this project, the scientific objectivity of the research or its integrity? Note: The Principal Investigator (Project Director), upon consideration of the individual's role and degree of independence in carrying out the work, will determine who is responsible for the design, conduct, or reporting of the research.

See Disclosures and Management of Personal Interests in Human Research

<http://www.yale.edu/hrpp/policies/index.html#COI>

09/29/12 Version 13

 Yes       No

Do you or does anyone on the research team who is determined by you to be responsible for the design, conduct or reporting of this research have any patent (sole right to make, use or sell an invention) or copyright (exclusive rights to an original work) interests related to this research protocol?

 Yes       No

If yes to either question above, list names of the investigator or responsible person:

*The Yale University Principal Investigator, all Yale University co-investigators, and all Yale University individuals who are responsible for the design, conduct or reporting of research must have a current financial disclosure form on file with the University's Conflict of Interest Office. Yale New Haven Hospital personnel who are listed as co-investigators on a protocol with a Yale University Principal Investigator must also have a current financial disclosure form on file with the University's Conflict of Interest Office. If this has not been done, the individual(s) should follow this link to the COI Office Website to complete the form: <http://www.yale.edu/coi/>*

**NOTE:** The requirement for maintaining a current disclosure form on file with the University's Conflict of Interest Office extends primarily to Yale University and Yale-New Haven Hospital personnel. **Whether or not they are required to maintain a disclosure form with the University's Conflict of Interest Office, all investigators and individuals deemed otherwise responsible by the PI who are listed on the protocol are required to disclose to the PI any interests that are specific to this protocol.**

## **SECTION II: GENERAL INFORMATION**

**1. Performing Organizations:** Identify the hospital, in-patient or outpatient facility, school or other agency that will serve as the location of the research. Choose all that apply:

**a. Internal Location[s] of the Study:**

- |   |   |
|---|---|
|  Magnetic Resonance Research Center (MR-TAC)                       |  Yale University PET Center        |
|  Yale Cancer Center/Clinical Trials Office (CTO)                              |  YCCI/Church Street Research Unit (CSRU)      |
|  Yale Cancer Center/Smilow  |  YCCI/Hospital Research Unit (HRU)            |
|  Yale-New Haven Hospital  |  YCCI/Keck Laboratories                       |
|  Cancer Data Repository/Tumor Registry  |  Yale-New Haven Hospital—Saint Raphael Campus |
|  Specify Other Yale Location: Alzheimer's disease research center. |   |

**b. External Location[s]:**

- |   |  |
|---|--|
|  APT Foundation, Inc.                       |  Haskins Laboratories                  |
|  Connecticut Mental Health Center           |  John B. Pierce Laboratory, Inc.       |
|  Clinical Neuroscience Research Unit (CNRU) |  Veterans Affairs Hospital, West Haven |

Other Locations, Specify:  International Research Site  
(Specify location(s)):

**c. Additional Required Documents (check all that apply):**

- |  |                              |
|--|------------------------------|
|  *YCCI-Scientific and Safety Committee (YCCI-SSC)  |  N/A |
|  *Pediatric Protocol Review Committee (PPRC)   | Approval Date:               |
|  *YCC Protocol Review Committee (YRC-PRC)  | Approval Date:               |
|  *Dept. of Veterans Affairs, West Haven VA HSS   | Approval Date:               |
|  *Radioactive Drug Research Committee (RDRC)  | Approval Date: Pending       |
|  YNHH-Radiation Safety Committee (YNHH-RSC)  | Approval Date:               |
|  Yale University RSC (YU-RSC)   | Approval Date: Pending       |
|  Magnetic5Resonance Research Center PRC (MRRC-PRC)  | Approval Date: 3/1/2017      |
|  *Nursing Research Committee   | Approval Date:               |
|  YSM/YNHH Cancer Data Repository (CaDR)  | Approval Date:               |
|  Dept. of Lab Medicine request for services or specimens form  |                              |
|  Imaging on YNHH Diagnostic Radiology equipment request form (YDRCTO request) found at http://radiology.yale.edu/research/ClinTrials.aspx |                              |

**\*Approval from these committees is required before final HIC approval is granted. See instructions for documents required for initial submission and approval of the protocol. Allow sufficient time for these requests. Check with the oversight body for their time requirements.**

**2. Probable Duration of Project:** State the expected duration of the project, including all follow-up and data analysis activities. **5 Years**

**3. Research Type/Phase: (Check all that apply)**

**a. Study Type**

- Single Center Study  
 Multi-Center Study

Does the Yale PI serve as the PI of the multi-site study? Yes  No

- Coordinating Center/Data Management  
 Other:

**b. Study Phase**  N/A

- Pilot  Phase I  Phase II  Phase III  Phase IV  
 Other (Specify)

**4. Area of Research: (Check all that apply)** Note that these are overlapping definitions and more than one category may apply to your research protocol. Definitions for the following can be found in the instructions section 4c:

- |   |  |
|---|--|
|  Clinical Research: Patient-Oriented                |  Clinical Research: Outcomes and Health Services |
|  Clinical Research: Epidemiologic and Behavioral    |  Interdisciplinary Research           |
|  Translational Research #1 ("Bench-to-Bedside")     |  Community-Based Research                        |
|  Translational Research #2 ("Bedside-to-Community") |  |

5. Is this study a clinical trial? Yes  No

*NOTE the current ICMJE (International Committee of Medical Journal Editors) definition of a clinical trial: "any research study that prospectively assigns human participants or groups of humans to one or more health-related interventions to evaluate the effects on health outcomes." Health-related interventions include any intervention used to modify a biomedical or health-related outcome (for example, drugs, surgical procedures, devices, behavioral treatments, dietary interventions, and process-of-care changes). Health outcomes include any biomedical or health-related measures obtained in patients or participants, including pharmacokinetic measures and adverse events"*

If yes, where is it registered?

Clinical Trials.gov registry

Other (Specify)

Registration of clinical trials at their initiation is required by the FDA, NIH and by the ICMJE.

*If this study is registered on clinicaltrials.gov, there is new language in the consent form and compound authorization that should be used.*

For more information on registering clinical trials, including whether your trial must be registered, see the YCCI webpage, <http://ycci.yale.edu/researchers/ors/registerstudy.aspx> or contact YCCI at [contact])

6. Does the Clinical Trials Agreement (CTA) require compliance with ICH GCP (E6)?

Yes  No

7. Will this study have a billable service? *A billable service is defined as any service rendered to a study subject that, if he/she was not on a study, would normally generate a bill from either Yale-New Haven Hospital or Yale Medical Group to the patient or the patient's insurer. The service may or may not be performed by the research staff on your study, but may be provided by professionals within either Yale-New Haven Hospital or Yale Medical Group (examples include x-rays, MRIs, CT scans, specimens sent to central labs, or specimens sent to pathology). Notes: 1. There is no distinction made whether the service is paid for by the subject or their insurance (Standard of Care) or by the study's funding mechanism (Research Sponsored). 2. This generally includes new services or orders placed in EPIC for research subjects.*

Yes  No

If answered, "yes", this study will need to be set up in OnCore, Yale's clinical research management system, for Epic to appropriately route research related charges. Please contact [[contact]](mailto:[contact])

8.. Are there any procedures involved in this protocol that will be performed at YNHH or one of its affiliated entities? Yes    No    *If Yes, please answer questions a through c and note instructions below. If No, proceed to Section III.*

- a. Does your YNHH privilege delineation currently include the **specific procedure** that you will perform? NO
- b. Will you be using any new equipment or equipment that you have not used in the past for this procedure?
- c. Will a novel approach using existing equipment be applied?

If you answered "no" to question 8a, or "yes" to question 8b or c, please contact the YNHH Department of Physician Services ([name]) for prior approval before commencing with your research protocol.

*Please note that if this protocol includes Yale-New Haven Hospital patients, including patients at the HRU, the Principal Investigator and any co-investigators who are physicians or mid-level practitioners (includes PAs, APRNs, psychologists and speech pathologists) who may have direct patient contact with patients on YNHH premises must have medical staff appointment and appropriate clinical privileges at YNHH. If you are uncertain whether the study personnel meet the criteria, please telephone the Physician Services Department at [contact]. By signing this protocol as a PI, you attest that you and any co-investigator who may have patient contact has a medical staff appointment and appropriate clinical privileges at YNHH.*

### SECTION III: FUNDING, RESEARCH TEAM AND TRAINING

**Funding Source:** See IRES-IRB

**Research Team:** See IRES-IRB

**Department Chair's Assurance Statement**

Do you know of any real or apparent institutional conflict of interest (e.g., Yale ownership of a sponsoring company, patents, licensure) associated with this research project?

Yes (provide a description of that interest in a separate letter addressed to the HIC.)

No

As Chair, do you have any real or apparent protocol-specific conflict of interest between yourself and the sponsor of the research project, or its competitor or any interest in any intervention and/or method tested in the project that might compromise this research project?

Yes (provide a description of that interest in a separate letter addressed to the HIC)

No

I assure the HIC that the principal investigator and all members of the research team are qualified by education, training, licensure and/or experience to assume participation in the conduct of this research trial. I also assure that the principal investigator has departmental support and sufficient resources to conduct this trial appropriately.

  
[name]

Chair Name (PRINT) and Signature

10/31/16

Date

Neurology  
Department**YNHH Human Subjects Protection Administrator Assurance Statement**

*Required when the study is conducted solely at YNHH by YNHH health care providers.*

As Human Subject Protection Administrator (HSPA) for YNHH, I certify that:

- I have read a copy of the protocol and approve it being conducted at YNHH.
- I agree to notify the IRB if I am aware of any real or apparent institutional conflict of interest.
- The principal investigator of this study is qualified to serve as P.I. and has the support of the hospital for this research project.

---

YNHH HSPA Name (PRINT) and Signature

---

Date**SECTION V: RESEARCH PLAN****1. Statement of Purpose:** State the scientific aim(s) of the study, or the hypotheses to be tested.

We have developed a functional test of brain microglial response that involves administering LPS (0.4 ng/kg) intravenously and measuring C-PBR28 binding (measured as volume of distribution or VT) at baseline and 180

minutes post LPS. We define microglia activation reserve index (MARI) as the proportional increase in binding of PBR28, 180 minutes after the administration of the LPS:  $MARI = [(VT(LPS)-VT(baseline))/ VT(baseline)] \times 100$ . In a previous study, we demonstrated the feasibility and robustness of this technique by applying this methodology to 8 healthy volunteers showing 30-60% increase in PBR28 binding after LPS administration (10). We predict increased MARI in patients with early AD compared to cognitively normal aged matched individuals. Given that we also have data from young healthy individuals from our earlier study, we can explore whether the microglia activation reserve index is increased in microglia with aging (which we predict to be the case). We can gauge also whether the changes in MARI in AD represent incremental increases compared to normal aging or that a significant dysregulation of innate immunity occurs in AD. With this experiment we aim to:

Aim - Examine the differences in the capacity to activate microglia in patients with AD compared to age-comparable cognitively normal subjects and younger healthy controls.

Hypothesis: In early AD the innate immune response becomes more reactive to PAMPs and DAMPs compared to those with normal cognition.

Our primary outcome is MARI (calculated in the parietal ROIs) in AD patients compared to elderly controls. We will use 7 AD and 7 comparably aged cognitively normal successfully scanned subjects to calculate the microglial activation reserve index. We expect significant differences between the two groups suggesting increased reactivity of the microglia in AD. The reverse would suggest a burn-out phenomenon which we expect to occur in a later stage of the disease but not in our study cohort. This result would be an exciting one suggesting at least one mechanism by which some patients with significant amyloid load have progressive dementia while comparable others are either cognitively normal or have stable MCI. It will also suggest avenues for intervention in amyloid positive MCIs to prevent progression to Alzheimer's dementia. Our exploratory analysis will include:

- a) Effects of aging on MARI: We will evaluate the effects of aging on MARI. Comparisons will be made for MARI between cognitively normal elderly and the 8 healthy individual to whom we applied this protocol in an earlier study. The reactivity of microglia is reported to increase with age (11) and so we expect MARI to increase in the cognitively normal elderly. However, we expect the differences between the young and elderly cognitively normal subjects to be small relative to the comparison of AD and elderly normal controls.
- b) Effects of amyloid on MARI: We will look at the relationship of regional and global amyloid load to MARI. The presence of a relationship suggests that one of the reasons for increased microglial reactivity might be interactions of microglia with pathologic amyloid.
- c) Effects of MARI on cognition: We will explore whether MARI would correlate with measure of disease stage, with higher MARIs associated with worse neuropsychological score and more severe disease. We will look for correlations between MARI and the individual neuropsychological scores. This would determine if disease severity is correlated with microglial activation reserve.

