**PET Imaging of TSPO in AD**

We will compare PBR28 binding site availability in brain regions of 7 living human subjects who have AD with that in 7 age-matched healthy controls by using the ligand  $^{11}\text{C}$ -PBR28 and PET. Dose of LPS (see below) will be administered intravenously and the subject will be reimaged at 180 minutes after the injection. Considering possible failures in scans, a total of 16 patients will be studied in 2 groups, cognitive normal AND amyloid negative versus clinical criteria for mild AD and amyloid positive to reach our goal of 7 successfully scanned subject for each group. The detailed protocol may be found

09/29/12 Version 13

in our previous publication (109). We expect that 20-30% of cognitively normal participants who receive amyloid scans under this protocol will be amyloid positive. Therefore, we will enroll up to 10 participants in the cognitively normal cohort to attain the goal of 7 participants who are cognitively normal AND amyloid negative.

Primary Outcome:

The 16 enrolled subjects will have C-PBR28 using the bolus/infusion method. Measurements will be made at baseline and 180 minutes after the injection of LPS. We will measure Total Volume of Distribution (VT) for 12 brain regions defined by MRI scan, as described (111). All primary outcomes will use the parietal ROI for calculations of both baseline activation and microglial activation reserve. For our primary outcomes we will choose the microglia activation reserve index defined as MARI =  $[(VT(LPS)-VT(\text{baseline}))/ VT(\text{baseline})] \times 100$ . In the NIMH study the greatest difference in the regional PBR28 binding between AD and cognitively normal subjects was found in the parietal lobe (7). We also found the greatest microglia activation reserve index in the parietal lobe when we applied our paradigm to young healthy controls (109). Other ROIs will be used in secondary analyses.

Statistical Considerations and Sample Size:

Several comparisons of C-PBR28 VT brain level and microglia activation reserve index in the parietal lobe will be made using Student T-test to test for a difference between group means: young healthy group vs. elderly cognitively normal, as well as AD vs. elderly cognitively normal.

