**Primary Outcome:**

The 16 enrolled subjects will have C-PBR28 using the bolus/infusion method. Measurements will be made at baseline and 180 minutes after the injection of LPS. We will measure Total Volume of Distribution (VT) for 12 brain regions defined by MRI scan, as described (111). All primary outcomes will use the parietal ROI for calculations of both baseline activation and microglial activation reserve. For our primary outcomes we will choose the microglia activation reserve index defined as MARI = [(VT(LPS)-VT(baseline))/ VT(baseline))] X %100. In the NIMH study the greatest difference in the regional PBR28 binding between AD and cognitively normal subjects was found in the parietal lobe (7). We also found the greatest microglia activation reserve index in the parietal lobe when we applied our paradigm to young healthy controls (109). Other ROIs will be used in secondary analyses.

Statistical Considerations and Sample Size: Several comparisons of C-PBR28 VT brain level and microglia activation reserve index in the parietal lobe will be made using Student T-test to test for a difference between group means: young healthy group vs. elderly cognitively normal, as well as AD vs. elderly cognitively normal. Although this is intended as a pilot study we have performed some basic power analyses. For the comparison of baseline activation in AD vs. aged matched cognitively normal subjects based on standard deviations derived from Kreisel (7) and our own previous studies (107,109,111), using an alpha of 0.05 and power of 0.80, our study is powered to detect an effect size of > 1.6 which is not far off from the findings in the NIMH study. For the comparison of percentage post-LPS change from baseline in AD and NC groups we are powered to detect an effect size of more than 2.

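### The plan asks whether the rise in MARI in AD goes beyond ageing, but names no analysis that compares the AD difference with the ageing difference

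*Combined protocol and SAP*

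**What the plan says.** Section V.1 (Statement of Purpose) says the young volunteers from an earlier study allow the team to judge "whether the changes in MARI in AD represent incremental increases compared to normal aging or that a significant dysregulation of innate immunity occurs in AD". Exploratory analysis (a) in the same section turns this into a statement about relative size: "we expect the differences between the young and elderly cognitively normal subjects to be small relative to the comparison of AD and elderly normal controls". It also says "Comparisons will be made for MARI between cognitively normal elderly and the 8 healthy individual" from the earlier study, and it predicts that MARI rises with age.

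The tests appear in Statistical Considerations and Sample Size (Section V.3) and again in the Statistical Considerations that follow the safety monitoring plan: "Student T-test to test for a difference between group means: young healthy group vs. elderly cognitively normal, as well as AD vs. elderly cognitively normal". The Expected Result, Interpretation and Secondary Analyses paragraphs add no three-group model, no contrast and no interval for the difference between the two differences. No text says how the two test results are to be turned into 'incremental' or 'dysregulation'.

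**The concern.** The two t-tests have the nulls 'elderly = young' and 'AD = elderly'. The question in Section V.1 has a third null: the two steps are equal. Nothing planned tests or estimates that.

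With only two p-values to hand, the natural shortcut is to call the result AD-specific when the AD test is significant and the ageing test is not. At 7 v 8 subjects, a non-significant ageing test says little about the size of the ageing effect. The tests also share the elderly mean with opposite signs, so a chance low elderly mean enlarges the AD difference and shrinks the ageing difference together. At stake is a mechanistic statement that the pilot would carry into the larger project mentioned under Pitfalls and Limitations.

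**Working it through.** **Inputs.** AD and elderly: "We will use 7 AD and 7 comparably aged cognitively normal successfully scanned subjects" (Section V.1). Young: 8, from the earlier study. Error rates: "using an alpha of 0.05 and power of 0.80". Sidedness is not stated; two-sided is assumed. The plan gives no SD for MARI, so steps are in SD units and equal SDs are assumed, then varied.

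**The plan's own figure.** For baseline binding the plan says "our study is powered to detect an effect size of > 1.6 which is not far off". A two-sample t-test with 7 per group, two-sided 5% and 80% power gives a detectable difference of 1.63 SD (power at 1.6 SD is 78.5%). The figure reproduces, which supports the two-sided reading. For MARI the plan states more than 2. The same inputs give 92.9% power at 2 SD, so that figure does not follow from them; nothing below depends on it.

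**Power of the ageing test (8 v 7).** 14.6% for a 0.5 SD difference and 43% for 1 SD.

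**Correlation of the two estimated steps.** Covariance = -1/7. Variances = 1/7 + 1/8 = 0.268 and 2/7 = 0.286. Correlation = -0.143 / sqrt(0.268 x 0.286) = -0.52.

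**How often the pattern arises when the steps are equal.** Monte Carlo, 400,000 trials per setting, normal data, equal SDs, 8/7/7, two pooled two-sided 5% t-tests. Event: AD above elderly and significant, elderly v young not significant.

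| Each true step (SD) | AD significant, ageing not |
|---|---|
| 0.5 | 12.9% |
| 0.8 | 23.8% |
| 1.0 | 28.7% |
| 1.1 | 29.4% (maximum) |
| 1.6 | 17.0% |
| 2.0 | 5.4% |
| 2.5 | 0.7% |

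The opposite pattern (ageing significant, AD not) peaks at 32.3%. Other group sizes move the 29.4% maximum to 27.6% (8/6/6), 30.7% (8/8/8) or 33.4% (8/10/10). The unequal SDs tried gave about 20% to 39%.

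**The direct contrast.** C = (AD - elderly) - (elderly - young) = AD - 2 x elderly + young.

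- SE = sqrt(1/7 + 4/7 + 1/8) = sqrt(0.839) = 0.916 SD.
- 95% CI half-width = t(19 df) x SE = 2.093 x 0.916 = 1.92 SD.
- With equal steps, a finding of 'AD step larger' occurs in 2.5% of trials at every step size.
- Power for a true difference between steps: 18% at 1 SD, 38% at 1.6 SD, 54% at 2 SD; 80% needs about 2.7 SD.

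**Sensitivity of the contrast to the young group.** Preliminary Results reports LPS at 1.0 ng/kg in the young men. Endotoxin Administration gives 0.4 ng/kg here. The Lipopolysaccharide Administration paragraph describes 0.4 ng/kg as the dose already used in the team's recent study. Assume, for illustration only, that the higher dose raises MARI in the young group by b SD. C then shifts by +b. With truly equal steps, the upper-tail error of the contrast becomes 7% (b = 0.5), 18% (b = 1) and 54% (b = 2), instead of 2.5%.

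**The case against.** A reader might infer that the plan will declare AD-specific dysregulation wrongly in up to 29% of trials. The documents do not support that. They nowhere say the question will be settled by one significant and one non-significant result. Section V.1 speaks of gauging, and analysis (a) speaks of relative size, which two estimates could describe. The plan predicts that MARI rises with age, which sits badly with a rule that needs a null ageing test. The 29% is also a maximum over an unknown step size; at the 2 SD the plan mentions for MARI it is about 5%.

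A second objection is that AD v age-comparable controls is already a comparison with normal ageing. The Rationale puts the aim that way, and the Interpretation paragraph never uses the young group. That protects the primary comparison. It does not cover the separate sentence that brings in the young data to tell incremental change from dysregulation. Equal steps is one reading of 'incremental', though analysis (a) does frame the matter as one difference against another.

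A third is that the contrast has little power and inherits the young group's lack of comparability. This stands. It limits what the contrast can prove, but it does not leave the two t-tests answering the question.

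**Conclusion.** The gap is real: a stated question has no analysis that addresses it, and no rule for reading the two tests together. If they were read by significance alone, equal steps would look like AD-specific dysregulation in about 13% of trials at 0.5 SD, at most 29% near 1.1 SD, and 5% at 2 SD. These rates assume that reading, normal data, equal SDs and 8/7/7 completed subjects.

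The consequence is limited to an exploratory question in a pilot. The primary AD v elderly test is untouched. It would also be too strong to infer that a contrast whose interval excludes zero would establish dysregulation. The young men (mean age 24.9 years) differ from a cohort aged 55-90 with about half women in sex and reported LPS dose as well as age, so the ageing step is not a clean ageing effect under either analysis.

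**What to change.** In Section V.1, exploratory analysis (a) and both statistical sections:

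- Fit one three-group linear model to parietal MARI and report (AD - elderly) - (elderly - young) with its 95% CI, labelled exploratory.
- State that a non-significant elderly v young test is not evidence of a small ageing effect.
- State that an interval excluding zero is not sufficient for a dysregulation claim, and name the differences in the young group (LPS dose as documented, all male).
- Reconcile the LPS dose passages in Preliminary Results, Endotoxin Administration and Lipopolysaccharide Administration.
- If the young data cannot be treated as comparable, delete the incremental-or-dysregulation sentence from Section V.1.

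The cost is one contrast on data already planned, plus wording; no extra subjects or scans. The claim becomes harder to make: power is about 54% even for a 2 SD difference between steps, and the interval will span nearly 4 SD (2 x 1.92).
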